| | Treatment will consist of single repeated doses of SNS-301 administered every 21 days for 3 doses. A traditional 3+3 dose-escalation schema will be used to determine the MTD of SNS-301 for the first 2 doses and a modified dose-escalation schema for the remaining dose. Planned doses of SNS-301 are 2.0×10^{10} , 1.0×10^{11} and 3.0×10^{11} particles per administration diluted to 1 mL and administered intradermally. Additional patients will be enrolled at the highest dose level until at least 6 patients can be evaluated even if no DLTs are observed at the dose. Planned treatment may continue for two additional doses of SNS-301 administered every 21 days. Serum and whole blood samples will be obtained on the day of study treatment, at Day 1, Day 8, Day 15, and Day 22 during the first cycle. For patients who continue to receive study treatment, biochemical and immunologic testing will continue every 21 days. |
| | The MTD will be determined over the first 21-day interval following a single dose of SNS-301 in 3 dose cohorts. The MTD will be considered the dose level lower than the dose producing \geq 2 DLTs in 3-6 patients. Patients who withdraw in cycle 1 for reasons other than safety or toxicity will be replaced. Any of the following, if judged to be associated with SNS-301 |

| (i.e., possibly-, probably-, or definitely related to), will be considered a DLT using the National Cancer Institute-Common Terminology Criteria for Adverse Events (NCI-CTCAE) Version 4.03: |
|--|
| 1) Grade 4 non-hematological toxicities (excluding alopecia) of any duration |
| Grade 3 non-hematologic (non-laboratory) toxicity lasting > 3 days despite optimal supportive care |
| 3) Any Grade 3 or Grade 4 non-hematologic laboratory value if: a). Medical intervention is required to treat the patient; b), the abnormality leads to hospitalization; c). The abnormality persists for >1 week. |
| 4) Grade 4 hematologic toxicity, other than those specified in criteria 5 and 6 below, lasting > 7 days |
| 5) Grade 3 or Grade 4 febrile neutropenia of any duration |
| 6) Grade 3 thrombocytopenia in combination with a grade 3 or greater blood and lymphatic system disorder |
| 7) Grade 3 AST or ALT that is associated with a grade 2 rise in bilirubin |
| The recommended Phase 2 dose (RP2D) will be defined as the highest dose administered if no MTD is observed. |

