| | regulatory immune processes. Other Safety: Safety will be evaluated by the incidence and severity of ASRs, changes in biochemical safety measures, general incidence and types of AEs, serious adverse events (SAEs), and other overt toxicities. |
| Number of patients/ centers: | This is a multi-center dose-escalation study with an extension study at the RP2D. Up to approximately 18 patients will be studied. |
| Randomization procedure: | The study is an open-label, dose-escalating, non-randomized Phase 1 clinical study with a dose extension phase. No randomization will be performed. |
| Inclusion criteria: | Signed and dated written Ethics Committee approved informed consent Men aged 21 to 85 years with a histologic diagnosis of prostate cancer with a biochemical relapse following definitive local therapy (RP or radiation therapy) Patients are not eligible or are unwilling to receive additional definitive therapy following relapse (either RP or radiation therapy) No prior cytotoxic chemotherapy for the current cancer Normal electrocardiogram (ECG) or ECG with no clinically significant findings as determined by the Principal Investigator Presence of biochemically relapsed prostate cancer defined as either: PSA > 2 ng/mL 1 year following initial definitive treatment for prostate cancer: or, 2) PSA doubling time (greater than 0.2 ng/mL) < 12 months; or, 3) PSA velocity > 2 ng/mL/year at any time following radical prostatectomy or radiation therapy. Positive expression of HAAH in either archived tumor tissue (if available) or fresh serum No clinical or radiologic evidence of distant metastatic disease as measured by pelvic MRI or CT scan in addition to bone scan. These studies will need to be performed within 56±7 days prior to the start of the study. No history of immunosuppressive disease. Active autoimmune disease is defined as any disease process that has specifically needed administration of immune suppressive and or cytoreductive therapy currently or within the last 1 year. No evidence of active autoimmune disease Able and willing to comply with all study procedures |

| Exclusion criteria: | 1 PSA doubling time of ≤ 3 months |
|---------------------|---|

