| Route of administration: | Intradermally: vaccine to be delivered by a single-use 3M [®] hollow micro structured transdermal system (hMTS) device. |
|--------------------------|---|
| Dose regimen: | Escalating doses of 2.0×10^{10} and 1.0×10^{11} particles will be administered to cohorts of 3 patients and 3.0×10^{11} particles will be administered to a cohort of 6 patients every 21 days to assess the MTD. The RP2D will be considered the MTD unless convincing safety, PD, or PK data suggest otherwise. At such a point, these data will be shared with the FDA and the RP2D will be changed or additional dose escalation cohorts will be proposed If needed. Additional patients will be enrolled at the highest dose level until at least 6 patients can be evaluated even if no DLTs are observed at the dose. |
| | Patients in the dose-escalation phase may continue to receive single doses of SNS-301 at their original dose level every 21 days or until the PSA doubling is < 90 days or unacceptable toxicity as determined by the Principal Investigator is observed (either for that patient or in their dose cohort). Once the MTD/RP2D is determined, patients receiving ongoing treatment may be escalated to that dose for subsequent treatments and receive a maximum of 9 injections. Patients who have received more than 9 injections due to the timing of the amendment limiting therapy to 6 months (9 doses), will be stopped at their last dose received and be followed for 6 months as with other patients. These subjects will continue to be followed for safety and biochemical PSA monitoring on a monthly basis for 6 months and are eligible to resume SNS-301 in case of increases in PSA doubling to < 90 days or other evidence of disease progression and decline in immunological parameters. |

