3.4 Study Rationale

Oncology trials frequently employ dose-escalation using a 3+3 schema; it is considered standard practice for determining the MTD of a particular study treatment in humans. The starting dose for such studies is usually calculated from the results of toxicology studies, which are often not performed in humans [8]. In this study, the starting dose and the subsequent dose escalations were determined from the results of a repeated dose toxicology study conducted in rats that evaluated the same 3 intradermal doses and dose frequency for the SNS-301 as proposed here. Only minimal toxicologic effects were observed in the animals at the higher two dose levels and these were resolved through the 2- and 4-week recovery periods (see Section 3.2).

The selection rationale for the specific dose levels proposed for this study is based on the in vivo results of this range of doses in mice and rats that have shown both immunogenicity and efficacy of the SNS-301 vaccine. The vaccine has demonstrated immunogenicity in rats by IgG antibody response to recombinant HAAH and to the recombinant bacteriophage HAAH- 1λ drug substance at each dose level, 2×10^{10} , 1×10^{11} and 3×10^{11} particles. This antibody response is both dose level-dependent and dose number-dependent. In mice, dose levels of approximately 2×10^{10} to 3×10^{11} particles have also demonstrated immunogenicity in a similar dose level- and dose number-response manner in multiple studies. Furthermore, SNS-301 vaccine doses up to 3×10^{11} particles have demonstrated inhibition of solid tumor growth and metastases in in vivo mouse tumor models with the mouse hepatocellular carcinoma cell line, BNLT3, and with the mouse breast cancer cell line, 4T1 and have demonstrated inhibition of metastases in a rat tumor model with the rat prostate cancer cell line, MLLB-2.

The dose-escalation phase will be conducted in patients with biochemically relapsed prostate cancer because this is a cancer that generally takes a long time to develop. Further, archived patient tumor tissue will be tested for the HAAH epitope before enrollment into the study; patients who do not test positive for the HAAH epitope in archived tissue or fresh serum

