5.1 Overall Study Design and Plan Description

Figure 1: Dose-escalation study design (3+3 schema)

Following informed consent and screening, archived prostate tumor tissue and patient serum will be tested for the expression of HAAH. Patients who test positive for HAAH expression in either archived tumor tissue or fresh serum may be continued in the study. Baseline biochemical testing (chemistry, complete blood count [CBC], coagulation panel, CH50, and PSA) will be obtained prior to study treatment administration.

Treatment will consist of single repeated doses of SNS-301 administered every 21 days. A traditional 3+3 dose-escalation schema will be used to determine the MTD of SNS-301 for the first 2 doses and a modified dose-escalation schema with 6 patients per dose level for the remaining dose. Planned doses of SNS-301 are 2.0×10^{10} , 1.0×10^{11} and 3.0×10^{11} particles per administration diluted to 1 mL and administered intradermally. Additional patients will be enrolled at the highest dose level until at least 6 patients can be evaluated even if no DLTs are observed at the dose. Planned treatment may continue for two additional doses of SNS-301 administered every 21 days. Serum and whole blood samples will be obtained on the day of study treatment administration (Day 1) and 21 days thereafter. In patients who continue to receive study treatment, biochemical and immunologic testing will continue every 21 days.

The MTD will be determined over the first 21-day interval following a single dose of SNS-301 in 3 consecutive dose cohorts. The MTD will be considered the dose level lower than that dose which produces ≥ 2 DLTs in 3 or 6 patients. A DLT will be considered a protocolspecified drug-related grade 3-4 (National Cancer Institute Common Terminology Criteria for Adverse Events [NCI-CTCAE] V 4.03) adverse experience) (Section 5.4.5.1). The RP2D will be the highest dose administered if no MTD is observed.

Dose cohorts will be enrolled sequentially.

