Once the MTD/RP2D is determined, patients receiving ongoing treatment may be escalated to that dose for subsequent treatments and receive a maximum of 9 injections. Patients who have received more than 9 injections due to the timing of the amendment limiting therapy to 6 months (9 doses), will be stopped at their last dose received and be followed for 6 months as with other patients. These subjects will continue to be followed for safety and biochemical PSA monitoring on a monthly basis for 6 months and are eligible to resume SNS-301 in case of increases in PSA doubling to < 90 days or other evidence of disease progression and decline in immunological parameters.

Pharmacodynamic:

Exploratory pharmacodynamic (PD) analysis will be performed using dose, vaccine-specific antibody response (geometric mean titer), antigen-specific T and B cell indices, and the relative expression of HAAH in each patient's tumor. The PD will be balanced and optimized to the degree of antigen-specific immune response and minimized for the production of regulatory immune processes.

Other Safety:

Safety endpoints will be evaluated by the incidence and severity of administration site reactions, changes in biochemical safety measures, general incidence and types of AEs, serious adverse events (SAEs), and other overt toxicities.

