6.1 Statistical and Analytical Plans

No formal statistical analysis will be performed, however, statistical derivation of all data will be derived by dose cohort and displayed for inspection.

For the dose-escalation phase of the study, cohorts of 3 or 6 patients will be screened, registered and treated at each dose level. The actual sample size may vary depending on the incidence of DLT during Cycle 1 at a given dose level. Once the MTD/RP2D is determined, additional patients may be accrued to provide for 6 patients in the MTD cohort. Approximately, 18 patients will be screened, registered and treated in the trial.

The primary safety analysis will assess MTD and AEs, clinical laboratory tests, and tolerability, based on the combined evaluation of immunogenicity and incidence of DLTs in each patient.

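### An MTD and default RP2D below 3.0 × 10^11 can be declared on 0/3 patients, because filling that level to six is optional and comes after the decision

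*Protocol*

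**What the plan says.** - **Escalation.** Under Protocol 5.3.5, a level with no DLT in its first three patients is passed. Three more patients are added only after one DLT in three, and the level then passes with at most 1/6.
- **MTD.** The synopsis says "The MTD will be considered the dose level lower than the dose producing" two or more DLTs. Protocol 5.1 and SAP section 4 say the same, counting DLTs in 3 or 6 patients. None of them sets a minimum number of patients at the MTD level itself.
- **RP2D.** The synopsis (Dose regimen) says: "The RP2D will be considered the MTD unless convincing safety, PD, or PK data suggest otherwise". Protocol 5.1 adds: "The RP2D will be the highest dose administered if no MTD is observed".
- **Cohort sizes.** For the two lower doses the synopsis says "particles will be administered to cohorts of 3 patients and" then gives six patients for 3.0 × 10^11. Protocol 5.3.1 and 5.3.5 require at least six evaluable patients at that top dose, with or without DLTs.
- **Top-up of a lower MTD level.** Protocol 6.1, repeated in the synopsis (Statistical analysis), says: "Once the MTD/RP2D is determined, additional patients may be accrued to provide for 6 patients in the MTD cohort".
- **Use of the result.** Protocol 5.1: "Once the MTD/RP2D is determined, patients receiving ongoing treatment may be escalated to that dose for subsequent treatments".
- **SAP.** Section 6.3 places derivation of the primary endpoints outside its scope.

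**The concern.** MTD and RP2D are primary endpoints (Protocol 4.2.1), yet the evidence required for them depends on how the trial ends. If no MTD is reached, the recommended dose must have six evaluable patients. If toxicity has just appeared one level up, where confirmation matters more, three patients are enough.

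The sponsor already has six in mind for an MTD cohort, but the text makes that optional and places it after the determination. Nothing requires the added patients to be observed before the dose is declared, or before ongoing patients are moved up to it. That second consequence arises only when the declared dose is 1.0 × 10^11, since no level lies below 2.0 × 10^10.

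**Working it through.** **The plan's own figure.** Three levels × 6 = 18, which matches the approximately 18 patients in Protocol 6.2. With no DLTs at all, the plan needs 3 + 3 + 6 = 12.

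**Precision at the declared dose** (one-sided 95% Clopper–Pearson upper limits):
- 0/3: 1 − 0.05^(1/3) = 63.2%
- 0/6: 1 − 0.05^(1/6) = 39.3%
- 1/6: solving (1−p)^6 + 6p(1−p)^5 = 0.05 gives 58.2%

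**How often this path occurs.** The documents give no expected DLT rates, so the rates p1/p2/p3 for the three levels are assumptions, shown as a range. Inputs from Protocol 5.3.5 and 5.1:
- Passing level 1 or 2 on 0/3: (1−p)^3
- Passing on 1/6: 3p(1−p)^5
- Otherwise the level is toxic; level 3 is toxic with ≥ 2 of 6
- A = P(0/3 at level 1) × P(level 2 toxic): 2.0 × 10^10 declared on three patients
- B = P(pass level 1) × P(0/3 at level 2) × P(level 3 toxic): 1.0 × 10^11 declared on three patients
- Overturn: o(p) = P(≥ 2 DLTs in the next 3) = 3p²(1−p) + p³
- Declared dose changed by a top-up: A·o(p1) + B·o(p2)

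*Worked case, 5/10/20%.*
- Level 1: P(0/3) = 0.95³ = 0.857; P(pass) = 0.857 + 0.116 = 0.973.
- Level 2: P(0/3) = 0.729; P(toxic) = 1 − 0.729 − 0.177 = 0.094.
- Level 3: P(toxic) = 1 − 0.262 − 0.393 = 0.345.
- A = 0.857 × 0.094 = 0.081; B = 0.973 × 0.729 × 0.345 = 0.245; A + B = 0.325 (before rounding of the terms).
- o(0.05) = 0.0073 and o(0.10) = 0.028, so changed = 0.0006 + 0.0068 = 0.0074.

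| Assumed DLT rates | A | B | On 3 patients (A+B) | Declared dose changed |
|---|---|---|---|---|
| 5/10/20% | 0.081 | 0.245 | 32.5% | 0.7% |
| 10/20/30% | 0.212 | 0.269 | 48.1% | 3.4% |
| 5/20/40% | 0.250 | 0.382 | 63.2% | 4.2% |
| 2/5/10% | 0.025 | 0.098 | 12.3% | 0.07% |
| Flat 5% | 0.023 | 0.027 | 5.0% | 0.04% |
| Flat 2% | 0.004 | 0.005 | 1.0% | 0.001% |

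Percentages are of all trials. Column B is also the share in which ongoing patients could be moved up to a dose supported by three patients: 24%, 27% and 38% in the first three rows.

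**Cost of a mandatory top-up.** Both lower levels need one (six extra patients) with probability P(0/3 at level 1) × P(0/3 at level 2) × P(level 3 toxic) × o(p2) = 0.6%, 2.2% and 3.5% in the first three rows. Mean extra patients = 3 × (A + B) + 3 × that probability = 1.0, 1.5 and 2.0; at flat 2% and 5% it is 0.03 and 0.15. The total never exceeds 18 evaluable.

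**The case against.** **This is a conventional 3+3, modified on purpose only at the top dose.** True: requiring six at the MTD is a choice among variants, and its absence is not an error. But the sponsor already names six for the MTD cohort, so the issue is when and whether that happens.

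**Toxicity is expected to be low.** Protocol 3.4 reports from the rat study: "Only minimal toxicologic effects were observed in the animals at the higher two dose levels". If that carries over, the path is rare and the top-up almost never changes the dose. This stands and limits the weight of the point. The 32.5–63% figures depend on assumed top-dose DLT rates of 20–40%, which no document supports.

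**The precision gain is partial.** It also stands that a level confirmed at 1/6 has an upper limit of 58%, little better than 63%. The 39% limit needs all six DLT-free. Given 0/3, the next three are DLT-free with probability 0.9³ = 73% at a true rate of 10%, and 0.8³ = 51% at 20%.

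**Other provisions may cover the gap.** The synopsis says: "This is a multi-center dose-escalation study with an extension study at the RP2D", but gives the extension no size or decision role. The review of the overall safety profile in 5.3.5 applies before doses are increased. Protocol 6.1 has the primary safety analysis assess the MTD, possibly with the added patients, but makes nothing wait for them.

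**A reader might infer that the plan is silent on what to do if the added patients have DLTs.** The documents do not support that. Applying the rule of ≥ 2 DLTs in 3 or 6 patients to the filled cohort moves the MTD down a level, and the synopsis override commits the sponsor to share convincing contrary data with the FDA and then change the RP2D or propose further cohorts. **A reader might also infer that a toxic first dose would be named RP2D** through the no-MTD clause. That is a strained literal reading: 5.3.5 discusses a missing MTD in terms of 3.0 × 10^11, and the safety override would apply.

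**Conclusion.** The point holds as a cheap improvement to consider. When an MTD is observed below 3.0 × 10^11, the text allows it and the default RP2D to be declared on 0/3, with no obligation to observe three more patients first. The main loss is precision at a primary endpoint. It would go too far to infer that the plan often selects the wrong dose: the declared dose would change in at most about 4% of trials in the rising scenarios, and in under 0.1% in the low-toxicity ones.

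The frequencies rest on assumed DLT rates and on independent patients; the upper limits and the reading of the rules do not depend on those rates. Figure 1 (the escalation scheme) was not visible in the copy reviewed, so the reading rests on the text. Confidence is medium.

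**What to change.** In the synopsis, Protocol 5.1, 5.3.5 and 6.1, and SAP section 4, add:

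> *If the level immediately below one with ≥ 2 DLTs (the candidate MTD) has only 3 DLT-evaluable patients, 3 more will be enrolled at that level before the MTD/RP2D is declared and before ongoing patients are escalated to it. The candidate is declared the MTD if no more than 1 of 6 has a DLT; otherwise the same step applies one level lower.*

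Replace the top-up sentence in Protocol 6.1 and the synopsis (Statistical analysis) with:

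> *Before the MTD/RP2D is declared, the candidate MTD level will be brought to six DLT-evaluable patients.*

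In the synopsis Dose regimen row, describe the cohorts of three as initial cohorts, and keep the safety/PD override. Optionally, state that no MTD or RP2D is declared if 2.0 × 10^10 has ≥ 2 DLTs.

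**Cost.** Zero to three more patients per lower level: on average about 1 to 2 in the rising scenarios and at most 0.15 at flat rates of 2–5%. The maximum is 18 evaluable patients, within the stated total. Treated patients may exceed 18 because cycle 1 withdrawals unrelated to safety are replaced. When a top-up is needed, the declaration waits at least one further 21-day window.

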6.2 Determination of Sample Size

Cohorts of 3 or 6 patients will be screened and treated at each dose level. The actual sample size may vary depending on the incidence of DLT during the first cycle at a given dose level. Approximately 18 patients will be included and treated in the trial.

7. Ethics

7.1 Institutional Review Board (IRB) / Ethics Committee

Before the start of the study, the study protocol, ICF, and/or other appropriate documents will be submitted to the IRB, in accordance with local legal requirements. It is the responsibility of the Investigator to ensure that all aspects of the IRB review are conducted in accordance

with current local and U.S. regulations. Sensei and the Investigator must inform each other in writing that all ethical and legal requirements have been met before the first patient is enrolled at the study site.

7.2 Ethical Conduct of the Study

The study will be conducted in accordance with the ethical principles of the current version of the Declaration of Helsinki. The Sponsor and Investigator will comply with their responsibilities as defined in 21 CFR 312.50-312.70 and International Conference on Harmonization Guidance for Industry: E6 Good Clinical Practice (April 1996).

7.3 Patient Information and Consent

The Investigator will obtain informed consent from each patient enrolled in the study, in accordance with the U.S. Food and Drug Administration (FDA) regulations 21 CFR 50.20 - 50.27 and the laws and regulations of the state in which the investigation is being conducted.

The IRB must approve the ICF to be used by the Investigator. It is the responsibility of the Investigator to ensure that informed consent is obtained from the patient or his/her guardian or legal representative before any activity or treatment is undertaken which is not part of routine care. This includes, but is not limited to, the performance of diagnostic, screening, or therapeutic procedures and the administration of the first dose of study treatment. The draft version of the ICF will be modified by each site and reviewed and approved in writing by Sensei prior to submission to the IRB. The terms of the consent and when it was obtained must also be documented in the patient's CRF. A second copy of the current ICF will be reviewed and signed by the patient to allow for patient re-screening on study if archived tumor tissue or fresh serum is initially negative for HAAH. Over this 6-month interval, PSA levels can be obtained and if they have increased appreciably from the original screening visit and HAAH is positive in serum or tumor tissue, the patient may be enrolled in the study. The same archived tumor tissue will not be retested.

Should a protocol amendment be made, the subject ICF may be revised to reflect the changes of the protocol. If the ICF is revised, it is the responsibility of the Investigator to ensure that an amended ICF is reviewed and approved by the IRB and signed by all subjects subsequently entered in the study.

7.4 **Protocol Amendments**

Neither the Investigator nor Sensei will alter this study protocol without obtaining the agreement of the other. Amendments will be made only in exceptional cases once the study has started at the discretion of Sensei with the agreement of the Investigator. Changes must be agreed to in writing, and signed, by all parties concerned. The changes then become part of the study protocol. Any changes in the protocol, even local/site requirements, will be written in an amendment. The IRB must be informed of amendments and, if necessary, approval must be sought for ethical aspects. Approval of amendments must also be obtained from the local regulatory authority, if necessary.

